Optimizing the postoperative recovery of arthroplasty patients is a key factor in the fast-track protocols and day-case initiatives. Investigations of the postoperative course after hip and knee arthroplasty has identified insufficient mobilization, muscle weakness and urinary retention to be frequent postoperative challenges. Especially early mobilization is crucial in achieving timely discharge and reducing the risk of thromboembolic events. These postoperative challenges can be related to the anaesthesia methods used in hip and knee arthroplasty, however, our knowledge on this subject is lacking.

Comparative studies between spinal anaesthesia (SA) and general anaesthesia (GA) suggest that GA may result in reduced length of stay, earlier mobilization, and less pain, while SA offers quicker post-anaesthesia care unit (PACU) discharge and less immediate postoperative pain. The choice between SA and GA lacks consensus among surgeons, with preferences varying based on individual or centre preferences. This current knowledge gap highlights the necessity for contemporary, detailed studies to inform optimal anaesthesia choices for hip and knee arthroplasty patients.

OBJECTIVES

The primary objective of this study is to compare the impact of spinal anaesthesia and general anaesthesia on early mobilization after total hip (THA), total knee (TKA) and unicompartmental knee arthroplasty (UKA).

Secondary objectives are to compare fulfilment of discharge criteria, postoperative nausea and vomiting, pain, and use of opioids after THA, TKA, and UKA anaesthetized using either SA or GA.

STUDY METHODS

TRIAL DESIGN

This study consists of three individual trials. Each trial examines different hip and knee arthroplasty populations, but has identical methods for inclusion, randomization, data collection and statistical analysis. The trials are named:

- Randomized trial on Spinal Anaesthesia vs. General Anaesthesia (SAGA) on recovery after total hip arthroplasty (RCT SAGA THA)
- Randomized trial on Spinal Anaesthesia vs. General Anaesthesia (SAGA) on recovery after total knee arthroplasty (RCT SAGA TKA)
- Randomized trial on Spinal Anaesthesia vs. General Anaesthesia (SAGA) on recovery after unicompartmental knee arthroplasty (RCT SAGA UKA)

Each trial is conducted as a pragmatic, multicentre, randomized (1:1), single-blinded, clinical trial. Participants are randomized to receive either 1) spinal anaesthesia (SA) or 2) general anaesthesia (GA). Study data is gathered continuously during admittance. Study personnel is blinded to the allocation of the patients, but clinical personnel and the patients are not blinded, as this is not feasible given the interventions.

RCT SAGA UKA is conducted as a pilot trial exclusively at Copenhagen University Hospital Hvidovre. RCT SAGA THA and RCT TKA are conducted as multicentre trials at both Copenhagen University Hospital Hvidovre and Lillebaelt Hospital – Vejle.

RANDOMIZATION

Permutated block-randomization (4 or 6), stratified by centre for RCT SAGA THA and TKA, with allocation disclosed using non-transparent envelopes. A designated person, at Clinical Orthopaedic Research Hvidovre, Copenhagen University Hospital Hvidovre, with no other relation to the project is responsible for generating randomization sequences and preparation of the envelopes. Included patients are randomised at least three days before their planned surgery date.

SAMPLE SIZE

v. 1.0

The primary endpoint of the study is whether patients are able to be safely mobilized during a 5meter walking test within 6 hours of surgery. In previous studies safe mobilization was achieved after GA for 95% of THA and TKA patients, while it was only achieved for 30-45% of THA and TKA patients after SA. For this study we decided on a minimal clinically relevant difference in proportions of 30%. To detect a clinically relevant difference between 60% achieving safe mobilization in one group and 90% of achieving safe mobilization in the other group within 6 hours, would require 32 patients in each arm of each trial (95% confidence, 80% power). We aim to include 37 participants to each arm of each trial, to allow for a 15% dropout-rate in each trial.

- RCT SAGA UKA: 74 participants (37 SA and 37 GA) all from Copenhagen University Hospital Hvidovre.
- RCT SAGA THA: 74 participants (37 SA and 37 GA) from Copenhagen University Hospital Hvidovre (intended nr. participants = 38) and Vejle Hospital (intended nr. participants = 36).
- RCT SAGA TKA: 74 participants (37 SA and 37 GA) from Copenhagen University Hospital Hvidovre (intended nr. participants = 38) and Vejle Hospital (intended nr. participants = 36).

If one centre experiences recruitment issues, randomisation envelopes in 1 or 2 blocks will be transferred to the other centre.

FRAMEWORK

Superiority of GA over SA in achieving safe mobilization within 6 hours of surgery will be claimed if a difference in proportions of 30% is found in favour of GA.

STATISTICAL INTERIM ANALYSES AND STOPPING GUIDANCE

No interim analyses are planned. The investigators will evaluate the occurrence of serious adverse events, and if these occur in an unexpectedly high proportion of patients in relation to one of the interventions, the study will be stopped.

TIMING OF FINAL ANALYSIS

The final analysis is conducted when all included patients in the trial have passed the last followup (30 days after surgery).

TIMING OF OUTCOME ASSESSMENTS

Primary endpoint: safe mobilization at 5-meter walking test within 4-6 hours postoperatively. Patients will be given until 6 hours postoperatively to complete the walking test, and any early failed attempts will be redone at 6 hours postoperatively.

Secondary endpoints: fulfilment of discharge criteria, postoperative nausea and vomiting, pain, and use of opioids are evaluated at 4 and 6 hours postoperatively on the day of surgery and at 10:00 and 18:00 on any following postoperative days if the patient is still admitted.

STATISTICAL PRINCIPLES

CONFIDENCE INTERVALS AND P-VALUES

Confidence level is set at 95%, and results are presented with 95% confidence intervals. No adjustments for multiplicity are made.

ADHERENCE AND PROTOCOL DEVIATIONS

If patients are anaesthetised differently than allocated (i.e., GA instead of SA, due to technical difficulties), this is registered, and data collection continues. Reasons for cross-over are registered and reported. The overall adherence within the intervention groups will be reported.

All protocol deviations regarding sample size, eligibility, randomization, intervention, outcome definitions and statistical analyses plan will be reported.

ANALYSIS POPULATIONS

Any cases of crossover between the intervention groups will be included in their allocated treatment group as part of a modified intention-to-treat (mITT) analysis. The mITT will exclude randomised patients that did not undergo the intended arthroplasty surgery in the SAGA setup:

- Patients that after randomisation, but before being told their treatment allocation, decided not to go through with the arthroplasty surgery at the hospital.
- Patients that after randomisation, but before being told their treatment allocation, withdrew consent to participate.
- Patients that after randomisation, but before receiving treatment, were found unsuited for inclusion based on inclusion and exclusion criteria or were not able to be operated in a standard setup in accordance with the SAGA protocol.

All patients are randomised at least 72 hours before surgery but are only informed of their treatment allocation in the operating room just before surgery. The research staff remains blinded. We do therefore not consider any of the above exclusions to be related to the treatment allocation, in line with recommendations regarding unbiased mITT analyses [1].

If patients withdrew their consent or declined surgery in the operating room after being told their allocation, they will be included in the mITT as a case with missing data in the primary endpoint, as we cannot consider this to be unrelated to the treatment allocation.

If cross over cases are present in the mITT population, a secondary per-protocol (PP) analysis will be conducted on the same population according to the actual treatment received. The mITT analysis will evaluate the postoperative recovery related to a setup with intended GA or SA, while a potential PP analysis will evaluate postoperative recovery based on receiving GA or SA. The mITT analysis will be the primary analysis of the studies.

TRIAL POPULATION

SCREENING DATA

Data on eligibility incl. age, sex and surgery type is collected and reported in aggregated form. This will function as a comparison between included and non-included patients. No statistical comparisons will be conducted.

ELIGIBILITY

Inclusion criteria:	Exclusion criteria:
 Clinical and radiological hip or knee osteoarthritis meeting the indications for primary THA, TKA or UKA 	• Lives in an institution
	 Uses walking aids, such as walker or a wheelchair.
• ≥18 years of age	• Terminal illness
 Able to speak and understand Danish 	 Has contraindications for either SA or GA
Able to give informed consent and must be cognitively intact	 Has objections to receiving either GA or SA
	 Requires anxiolytics as premedication prior to anaesthesia
	 Traumatic aetiology as a basis for surgical indication
	 Altered pain perception and / or neurologic affection due to diabetes or other disorders
	 Daily preoperative use of opioids > 30 mg of morphine milligram equivalents (MME)
	 Standard primary arthroplasty procedure is evaluated not to be suitable
	 Women considered fertile but without sufficient birth control

RECRUITMENT, WITHDRAWAL AND FOLLOW-UP

Patients are pre-screened by the orthopaedic surgeons. At a standard preoperative physical examination 2-3 week prior to surgery, patients are asked whether research personnel can contact patients to provide them with study information. If patients consent to participation, the anaesthesiologist at the following standard preoperative anaesthesiologic examination will screen the patient for any contraindications for either SA or GA. Once screened by the anaesthesiologists, patients are considered included in the studies and baseline characteristics will be recorded.

Should the investigators become aware of previously unknown conditions, making included patients ineligible for participation, the investigators will withdraw the patient. These conditions include but are not limited to worsening of known disease, newly developed diseases or health conditions, and general safety concerns regarding anaesthesia.

In a CONSORT flow diagram the following will be reported; number of screened patients, number of excluded patients, number of randomized patients, number of patients allocated to each trial arm, number of patients that received anaesthesia in accordance with the allocation, and the number of patients that, after randomization, withdrew their consent, were excluded, or lost to follow-up.

BASELINE CHARACTERISTICS

The following baseline characteristics are registered at the time of inclusion:

Age, sex, height, weight, Charlson Comorbidity Index, Pain Catastrophizing Scale score, FRAILscale, ASA-score, preoperative blood sample results.

The baseline characteristics will be presented by intervention group using descriptive statistics. No statistical testing will be performed for baseline differences as suggested by the CONSORT-group [2].

ANALYSIS

OUTCOME DEFINITIONS

PRIMARY OUTCOME:

Ability to walk 5 meters 6 hours postoperatively:

Whether or not the participant is able to walk 5 meters safely and independently (also when using walking aid) within 6 hours of surgery evaluated by physiotherapists postoperatively.

Primary goal: Stable and safe 2-point gait with two crutches.

Secondary goal: Stable and safe 3-point gait with two crutches.

- Negative criteria:
 - Orthostatic: Dizziness, nausea, vomiting, fainting.
 - Motor control criteria: Poor muscle control or strength, insecure foot placement, impaired sensibility.

Stepwise mobilization course:

- Orthostatic test: from lying to sitting position.
- Motor control test: ability to move toes and lower limbs, firmly and securely planting the feet in the ground.
- Mobilization test: a few steps with a high walking frame.
- 5-Meter walking test using two crutches.

KEY SECONDARY OUTCOMES:

The key secondary outcomes are based on the first public registration of the study on https://euclinicaltrials.eu/ (2022-501221-21-00). Any erroneous disagreement between this first registration and the following registrations are corrected to coincide with the first registration.

Fulfilment of discharge criteria at 6 hours postoperatively:

v. 1.0

Fulfilment of functional discharge criteria is evaluated at both 4 and 6 hours postoperatively. This will be a dichotomous outcome where patients are either ready for discharge (fulfil all criteria) or are not ready for discharge (fail at least one criteria).

Pain levels at 4 and 6 hours postoperatively:

Pain levels (numerical relation scale (NRS) 0-10) during rest and activity (walking 5 meters) at 4 and 6 hours are registered through a nurse-assisted questionnaire.

Opioid use in Morphine Milligram Equivalents within the first 6 hours of surgery:

A cumulated amount of opioid in Morphine Milligram Equivalents within the first 6 hours postoperatively. Data on opioid use at the postoperative care unit and the bed ward is collected until 6 hours postoperatively.

Postoperative Nausea and Vomiting (PONV) at 4 and 6 hours postoperatively:

Nausea and vomiting levels (NRS 0-10) during rest and activity (walking 5 meters) at 4 and 6 hours are registered through a nurse-assisted questionnaire.

OTHER SECONDARY OUTCOMES:

Urinary retention: no spontaneous urination and bladder scan with >800 mL (>600 mL at Vejle) prior to discharge.

Vital signs: systolic and diastolic blood pressure, pulse, blood oxygen saturation, temperature. Postoperative blood sample results: Haemoglobin, serum-creatinine, and C-reactive protein. Opioid-Related Symptom Distress Scale – questionnaire (ORSDS): A score based on 20 opioid related symptoms evaluating the burden of these symptoms.

v. 1.0

Quality of Recovery – 15 score (QoR-15): a score based on 15 questions evaluating postoperative recovery.

3-minute Diagnostic Interview – Confusion Assessment Method (3D-CAM):

Attitude towards anaesthesia type: Whether patients would like to receive similar anaesthesia for any following arthroplasty surgery.

Blood transfusions: Whether patients received blood transfusion.

Emergency room contacts, complications, readmission or mortality within 30 days of surgery.

ANALYSIS METHODS

The primary analysis aim is to assess whether the ability to be safely mobilized within 6 hours of hip and knee arthroplasty is different between the two anesthetic methods, GA and SA. The main hypothesis to be tested is that GA patients are more likely to be safely mobilized compared to SA patients within 6 hours of arthroplasty surgery. This will be assessed in the (mITT) population, defined as all patients having undergone the intended arthroplasty surgery, between the comparison groups (GA and SA) as allocated. Superiority of GA over SA in achieving safe mobilization within 6 hours of surgery will be claimed if a difference in proportions of 30% is found in favour of GA.

Main analysis of primary outcome: The proportion of patients able to be safely mobilized within 6 hours of surgery will be compared between intervention groups using a logistic regression model. A supporting model adjusted, including possible confounders such as age and sex, will also be conducted. Estimates from the analysis will be presented as odd-ratios and 95% confidence intervals, for both crude and adjusted models.

In case of cross-over cases, a per-protocol analysis with similar statistical methods will be conducted.

Key secondary continuous outcomes will be analysed using t-test or Wilcoxon rank-sum test depending on normality. Results from t-tests will be presented as differences in means and 95%

confidence interval. Results from Wilcoxon rank-sum tests will be presented as differences in medians and p-values. Key secondary dichotomous outcomes will be compared using fisher's exact test. A mixed-effect model accounting for repeated measures using patient ID as a random effect will be used to compare both 4 and 6 hours NRS scores for pain and PONV between the intervention groups.

Normality will be evaluated using quantile-quantile plots and histograms.

MISSING DATA

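### 37 per arm does not quite cover the stated 15% dropout: keeping 32 evaluable needs 38, and 37 allows for 13.5% (a minor correction)

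*SAP*

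**What the plan says.** All the figures are in the Sample Size section of the SAP. For the 6-hour primary endpoint, the design target is given as "To detect a clinically relevant difference between 60% achieving safe mobilization in one group and 90% of achieving safe mobilization in the other group", and the SAP says that this "would require 32 patients in each arm of each trial (95% confidence, 80% power"). The next sentence moves from the number required to the number enrolled: "We aim to include 37 participants to each arm of each trial, to allow for a 15% dropout-rate in each trial".

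The same 37 is carried into the list of trials, for example "RCT SAGA UKA: 74 participants (37 SA and 37 GA) all from Copenhagen University Hospital Hvidovre". The hip (THA) and total knee (TKA) trials have the same 37 + 37, split over two centres. Allocation is equal (Trial Design: "randomized (1:1), single-blinded, clinical trial").

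The SAP does not show how 37 was obtained from 32, and it does not say whether the test behind the 32 is one-sided or two-sided.

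**The concern.** A dropout rate is a share of the patients enrolled. An allowance of 15% therefore means that 85% of the enrolled number must still reach the required number. With 37 enrolled and 32 required, that condition narrowly fails.

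What is at stake is the accuracy of a stated design property. The allowance has to absorb two kinds of loss that the SAP describes elsewhere: patients removed from the modified intention-to-treat population after randomisation (Analysis Populations), and patients in that population without a primary outcome (Missing Data). The SAP also undertakes to report protocol deviations regarding sample size (Adherence and Protocol Deviations), so the tolerance against which losses will be judged should be stated correctly.

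**Working it through.** **Inputs, from Sample Size and Trial Design.** Proportions 0.60 and 0.90, difference 0.30; 95% confidence; 80% power; 1:1 allocation; 32 required per arm; 15% dropout; 37 enrolled per arm. Two-sided testing at 5% is an assumption.

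**Step 1. Reproduce the 32.** Pooled two-proportion formula without continuity correction, mean proportion 0.75:

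n = [z(0.975) x sqrt(2 x 0.75 x 0.25) + z(0.80) x sqrt(0.6 x 0.4 + 0.9 x 0.1)]² / 0.30²

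= (1.2002 + 0.4835)² / 0.09 = 31.498, rounded up to 32.

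This matches the SAP. Variants do not: one-sided gives 25, unpooled variance 28.8, arcsine 29.8 and continuity-corrected 38. So the two-sided assumption is reasonable.

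**Step 2. Apply the 15% loss to 37.** 37 x 0.85 = 31.45 per arm, or 74 x 0.85 = 62.9 per trial, against 32 and 64. The shortfall is 32 - 31.45 = 0.55 of a patient per arm.

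**Step 3. Enrolment that would keep 32 after a 15% loss.** 32/(1 - 0.15) = 37.65, rounded up to 38 per arm, 76 per trial.

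**Step 4. Loss that 37 does cover.** 1 - 32/37 = 5/37 = 13.5%.

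**Step 5. Does the unrounded requirement rescue 37?** 31.498/0.85 = 37.06. Rounded up, as was done to reach 32, this again gives 38. Equivalently, 31.45 is below 31.498, though by only 0.05 of a patient.

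**Step 6. Effect on power.** Power = Φ{[0.30 x sqrt(n) - 1.2002] / sqrt(0.33)}, where sqrt(0.33) = 0.5745.

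| Evaluable per arm | Power |
|---|---|
| 31 | 79.3% |
| 31.45 (37 less 15%) | 79.9% |
| 32 | 80.6% |
| 37 (no loss) | 86.2% |
| 38 (no loss) | 87.1% |

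**Step 7. Is the choice of test a separate matter?** Exact power at 60% versus 90%, by enumerating both binomial distributions, two-sided 5%:

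| Test | 31 per arm | 32 per arm |
|---|---|---|
| Score (chi-square) | 81.3% | 82.8% |
| Likelihood ratio | 82.9% | 82.8% |
| Wald (logistic coefficient) | 74.9% | 77.0% |
| Fisher's exact | 72.7% | 74.8% |

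The tests that fall below 80% at 31 also fall below it at 32.

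**The case against.** The strongest reply is that nothing of substance is at stake. A dropout rate is a round planning guess, the gap is about half a patient per arm, and power at the stated dropout is 79.9% against 80%. The 15% is not used in any analysis. The SAP gives no expected rate of exclusions or missing outcomes, so nothing shows that losses would exceed five per arm. All of this stands, and it is why the point is minor. It does not make the sentence correct: 37 falls short whether one starts from 32 or from 31.498.

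Three stronger readings are tempting, and the SAP does not support them.

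- *That 32 was multiplied by 1.15 instead of divided by 0.85.* The figure 37 is consistent with this, since 32 x 1.15 = 36.8. But it also follows from rounding 37.65 down, or from rounding 37.06 to the nearest whole number. No formula is shown, so the cause remains an inference, and the point does not depend on it.
- *That the dropout allowance puts the 80% power at risk for some tests.* Step 7 shows that Wald and Fisher are already below 80% at the SAP's own 32 per arm. That gap comes from the choice of test. Fisher's test is in any case assigned to the key secondary dichotomous outcomes; the primary outcome uses logistic regression (Analysis Methods).
- *That the shortfall should be added up over the three trials.* They are three individual trials, each with its own sample size, so the relevant size is the one within each trial.

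**Conclusion.** The point holds as a minor arithmetic correction. Enrolling 37 per arm covers a 13.5% loss, not 15%; the number matching 15% is 38 per arm. The comparison of 31.45 with 32 uses only the SAP's own figures and needs no assumption beyond reading the dropout rate as a share of those enrolled. The power figures rest in addition on a two-sided 5% test, the pooled formula and true proportions of 60% and 90%. On that basis the effect on power is negligible, and no estimate, test, analysis population or conclusion depends on it.

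**What to change.** Restate the sentence in Sample Size along these lines: *37 per arm allows for 13.5% dropout (5 per arm); at 15% dropout about 31 per arm remain, with power of about 79-80% by the pooled two-proportion formula (two-sided 5%).* State the formula and the sidedness there, so that both 32 and the allowance can be checked.

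The cost is one sentence and a slightly less favourable stated tolerance. No extra enrolment is needed. If the sponsor prefers to keep the 15%, the matching figures are 38 per arm and 76 per trial, which is two more patients in each trial.

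### Superiority requires an observed 30-point difference, so at the design rates (60% vs 90%) the chance of claiming it is about one half, not 80%, and the primary outcome is reported only as odds ratios

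*SAP*

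**What the plan says.** Under Sample Size, 30 percentage points is set as the minimal clinically relevant difference ("we decided on a minimal clinically relevant difference in proportions of 30" percent). The calculation is for "a clinically relevant difference between 60% achieving safe mobilization in one group and 90% of achieving safe mobilization in the other group", which the SAP says "would require 32 patients in each arm of each trial (95% confidence, 80% power"). Enrolment is 37 per arm to allow for 15% dropout.

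Under Framework, superiority of GA "will be claimed if a difference in proportions of 30% is found in favour of GA". Analysis Methods repeats the sentence. Neither place attaches a p-value or confidence limit to the claim, and no other criterion for claiming superiority appears in the document.

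The main analysis of the primary outcome is a logistic regression. "Estimates from the analysis will be presented as odd-ratios and 95% confidence intervals", for crude and adjusted models. No risk difference, and no interval for one, is planned for the primary outcome.

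**The concern.** A difference used to size a trial and a threshold that the estimate must reach are different things. If the true difference equals the threshold, the estimate falls on either side of it about equally often, whatever the sample size. A trial with 80% power to reject no difference at a true 30 points therefore has only about an even chance of observing at least 30 points.

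Three things are at stake in each of the three trials:

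- The stated 80% power does not belong to the stated decision rule.
- A trial can show a significant odds ratio for GA and still fail the rule, and the SAP does not say which governs.
- The Missing Data section chooses the main result according to whether the conclusion differs across three analyses. That needs one unambiguous rule for reaching a conclusion.

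**Working it through.** **Inputs.** From Sample Size: 60% and 90%, 95% confidence, 80% power, 32 per arm, 37 per arm with dropout. From Trial Design: 1:1 allocation. From Framework and Analysis Methods: claim if the observed difference is 30 points. Assumption: the 5% level is two-sided. The SAP does not say so here, but a two-sided level reproduces its figure.

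**Step 1: the plan's own figure.** With pooled variance and p̄ = 0.75,

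n = [1.96·√(2·0.75·0.25) + 0.8416·√(0.60·0.40 + 0.90·0.10)]² / 0.30² = 31.5, rounded up to 32.

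This matches the SAP. The formula power is 80.6% at 32 per arm and 86.2% at 37. A one-sided test would need 25 per arm. So the 80% belongs to a two-sided 5% test of no difference.

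**Step 2: the written rule.** Let X be successes in SA, Binomial(n, 0.60), and Y successes in GA, Binomial(n, 0.90), independent. The probability of a claim is the sum of P(X = i)·P(Y = j) over all pairs with (j − i)/n ≥ 0.30. On whole counts the rule needs 10 extra successes at 32 per arm (10/32 = 31.3 points) and 12 at 37 per arm (12/37 = 32.4 points).

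| True SA vs GA | n per arm | Rule met | Pooled z-test favours GA |
|---|---|---|---|
| 60% vs 90% (design) | 32 | 0.514 | 0.828 |
| 60% vs 90% (design) | 37 | 0.456 | 0.875 |
| 65% vs 90% | 37 | 0.26 | 0.76 |
| 45% vs 95% (earlier studies) | 32 | 0.98 | >0.99 |
| 45% vs 95% (earlier studies) | 37 | 0.98 | >0.99 |

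Across equal arm sizes from 30 to 37 at the design rates, the rule is met with probability 0.46 to 0.56. It does not rise steadily with n, because the 30% cut falls unevenly on whole counts.

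**Step 3: adding significance.** Requiring 30 points and a significant z-test together gives the same 0.514 and 0.456, because every outcome that meets the rule at these sizes is also significant. At 37 per arm, 0.875 − 0.456 = 0.419, so about 42% of trials at the design rates would be significant for GA yet unable to claim superiority.

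**Step 4: false claims.** With equal true rates of 60% to 75% in both arms, the rule claims GA superiority in 0.1% to 0.7% of trials, against a nominal one-sided 2.5%. The rule is strict, not lax.

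**Step 5: a concrete result.** Take 22/37 in SA and 33/37 in GA, a difference of 11/37 = 29.7 points. The crude odds ratio is (33/4)/(22/15) = 5.6. The standard error of its log is √(1/33 + 1/4 + 1/22 + 1/15) = 0.626, giving a 95% CI of 1.65 to 19.2. The planned analysis shows a clear advantage for GA, and the rule, read exactly, is not met.

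**Step 6: the odds ratio at the boundary.** If every GA patient succeeds, the crude odds ratio is infinite and a Wald interval is unusable. At the 95% GA rate cited under Sample Size, this has probability 0.95³² = 0.19 or 0.95³⁷ = 0.15 per trial. At the design rate of 90% it is 0.90³² = 0.03 or 0.90³⁷ = 0.02.

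**The case against.** The strongest reply is that the SAP says superiority is claimed if 30 points is found, not only if. It also states a hypothesis, a 95% confidence level and a logistic model with intervals, so a conventional test may be what was meant, and for that test 80% is correct. This does not rescue the text. The 30-point sentence is the only criterion for a claim, it appears twice, and the confidence level is a general reporting statement not tied to it. If a test was intended, the SAP must say so.

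A second reply is that a sponsor may choose a strict relevance bar, and that this one does not inflate false claims. Both are true, but the stated power would then be wrong for the chosen rule.

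Several limits on the point do stand:

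- At the rates cited from earlier studies the rule is met at least 98% of the time. The shortfall is at the rates used for sizing and at smaller effects.
- If 11/37 = 29.7 points is rounded and accepted as 30%, the probability at 37 per arm is 0.57, not 0.456.
- The smallest significant differences are borderline. For 22/37 vs 30/37 (21.6 points), z = 2.03, but Fisher's p is 0.074 and the Newcombe lower limit is 0.008.
- The odds ratio and the risk difference always agree in sign. The conflict is only a significant odds ratio without a claim.
- The observed difference is easy to calculate. What is missing is a planned interval for it.
- The infinite odds ratio is mainly a concern at 95% success, not at 90%, and the SAP does not specify Wald intervals.

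**Conclusion.** The concern holds. As written, the decision rule and the power statement describe different procedures. At the SAP's own design alternative the chance of claiming superiority is 51% at 32 per arm and 46% at 37 per arm, or 57% at 37 per arm if 29.7 points is counted as 30%. It is not the stated 80%. A 5% test on the same data would succeed in 83% and 87% of trials. The calculation assumes independent binomial outcomes, equal arms, a two-sided 5% level, and the 30-point sentence as the sole criterion. The error is conservative: it costs power and leaves the conclusion open when the odds ratio is significant but the difference is below 30 points. Because it governs the main conclusion of all three trials, it should be corrected before analysis.

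**What to change.** In Framework and in Analysis Methods, replace the sentence with: superiority of GA is claimed if the two-sided 95% confidence interval for the risk difference (GA minus SA) lies above 0. Name the interval method, for example Newcombe, or Mantel-Haenszel stratified by centre in the THA and TKA trials. With the Newcombe interval the exact power at 60% vs 90% is 0.827 at 32 per arm and 0.875 at 37 per arm, so the existing sample size supports this rule.

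State separately how the estimate and its interval will be compared with the 30-point minimal clinically relevant difference. Make the risk difference the primary estimate and keep the logistic odds ratio as supportive, using Firth or profile-likelihood intervals if an arm has 0% or 100% success. The choice of interval method is a preference. The minimum is one sentence tying the claim to the interval or p-value of the planned analysis, with the risk difference also reported.

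If the 30-point rule is to stay, restate the power at 60% vs 90% as roughly one half (46% to 51% read exactly, up to 57% with rounding) and say how a difference just under 30 points is treated.

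The cost is wording in two places and one line of R code, with no extra patients or data.
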